9.4.7 SUB-GROUP ANALYSES

There is no reason to suspect that age, sex, race/ethnicity will influence our primary or secondary outcomes, particularly because we have not found these factors in prior endothelial keratoplasty studies including DETECT-TES.

9.4.8 TABULATION OF INDIVIDUAL PARTICIPANT DATA

Participant data will be listed by measure and time point.

9.4.9 EXPLORATORY ANALYSES

Tertiary outcomes

The effect of endothelial keratoplasty on refractive outcomes will be evaluated using the baseline refraction

10 SUPPORTING DOCUMENTATION AND OPERATIONAL CONSIDERATIONS

10.1 REGULATORY, ETHICAL, AND STUDY OVERSIGHT CONSIDERATIONS

10.1.1 INFORMED CONSENT PROCESS

10.1.5.1 CONSENT/ASSENT AND OTHER INFORMATIONAL DOCUMENTS PROVIDED TO PARTICIPANTS

Consent forms describing in detail the study interventions, study procedures, and risks are given to the participant and written documentation of informed consent is required prior to starting intervention/administering study intervention.

Prior to initiating the informed consent process, enrolling clinicians will assess patient decisional and cognitive ability through review of the following questions:

- Does the patient understand the study?
- Were the patient's questions answered?
- Is the patient willing to participate?
- Does the patient have the ability to make this decision?

If the answer to any question is "no," the patient will not be enrolled in the study. If the clinician can answer "yes" to all of the above questions, he/she will proceed with the informed consent process.

10.1.5.1 CONSENT PROCEDURES AND DOCUMENTATION

Informed consent is a process that is initiated prior to the individual's agreeing to participate in the study and continues throughout the individual's study participation. Consent forms will be Institutional Review Board (IRB)-approved and the participant will be asked to read and review the document. The investigator will explain the research study to the participant and answer any questions that may arise. A verbal explanation will be provided in terms suited to the participant's comprehension of the purposes, procedures, and potential risks of the study and of their rights as research participants. Participants will have the opportunity to carefully review the written consent form and ask questions prior to signing. The participants should have the opportunity to discuss the study with their family or surrogates or think about it prior to agreeing to participate. The participant will sign the informed consent document prior to any procedures being done specifically for the study. Participants must be informed that participation is voluntary and that they may withdraw from the study at any time, without prejudice. A copy of the informed consent document will be given to the participants for their records. The informed consent process will be conducted and documented in the source document (including the date), and the form signed, before the participant undergoes any study-specific procedures. The rights and welfare of the participants will be protected by emphasizing to them that the quality of their medical care will not be adversely affected if they decline to participate in this study.

DETECT

Version 5.0
21 March 2023

10.1.2 STUDY DISCONTINUATION AND CLOSURE

This study may be temporarily suspended or prematurely terminated if there is sufficient reasonable cause. Written notification, documenting the reason for study suspension or termination, will be provided by the suspending or terminating party to study participants, investigator, funding agency, sponsor, and regulatory authorities. If the study is prematurely terminated or suspended, the Principal Investigator (PI) will promptly inform study participants, WCG IRB, and sponsor and will provide the reason(s) for the termination or suspension. Study participants will be contacted, as applicable, and be informed of changes to study visit schedule.

Circumstances that may warrant termination or suspension include, but are not limited to:

- Determination of unexpected, significant, or unacceptable risk to participants
- Demonstration of efficacy that would warrant stopping
- Insufficient compliance to protocol requirements
- Data that are not sufficiently complete and/or evaluable
- Determination that the primary endpoint has been met
- Determination of futility

Study may resume once concerns about safety, protocol compliance, and data quality are addressed, and satisfy the sponsor, WCG IRB, and/or Food and Drug Administration (FDA).

10.1.3 CONFIDENTIALITY AND PRIVACY

Participant confidentiality and privacy is strictly held in trust by the participating investigators, their staff, and the sponsor(s) and their interventions. This confidentiality is extended to cover testing of biological samples and genetic tests in addition to the clinical information relating to participants. Therefore, the study protocol, documentation, data, and all other information generated will be held in strict confidence. No information concerning the study or the data will be released to any unauthorized third party without prior written approval of the sponsor.

All research activities will be conducted in as private a setting as possible.

The study monitor, other authorized representatives of the sponsor, representatives of the Institutional Review Board (IRB), regulatory agencies or pharmaceutical company supplying study product may inspect all documents and records required to be maintained by the investigator, including but not limited to, medical records (office, clinic, or hospital) and pharmacy records for the participants in this study. The clinical study site will permit access to such records.

The study participant's contact information will be securely stored at each clinical site for internal use during the study. At the end of the study, all records will continue to be kept in a secure location for as long a period as dictated by the reviewing IRB, Institutional policies, or sponsor requirements.

Study participant research data, which is for purposes of statistical analysis and scientific reporting, will be transmitted to and stored at the Data Coordinating Center. This will not include the participant's contact or identifying information. Rather, individual participants and their research data will be identified by a unique study identification number. The study data entry and study management systems used by clinical sites and by the Data Coordinating Center research staff will be secured and password protected. At the end of the study, all study databases will be de-identified and archived at the Data Coordinating Center at UCSF.

Certificate of Confidentiality

To further protect the privacy of study participants, a Certificate of Confidentiality will be issued by the National Institutes of Health (NIH). This certificate protects identifiable research information from forced disclosure. It allows the investigator and others who have access to research records to refuse to disclose identifying information on research participation in any civil, criminal, administrative, legislative, or other proceeding, whether at the federal, state, or local

DETECT

Version 5.0
21 March 2023

level. By protecting researchers and institutions from being compelled to disclose information that would identify research participants, Certificates of Confidentiality help achieve the research objectives and promote participation in studies by helping assure confidentiality and privacy to participants.

10.1.4 FUTURE USE OF STORED SPECIMENS AND DATA

Data collected for this study will be analyzed and stored at the Data Coordinating Center at UCSF. After the study is completed, the de-identified, archived data will be transmitted to and stored on the Research Electronic Data Capture system (REDCap).

[figure not shown]
When the study is completed, access to study data will be provided through REDCap.

CIARC is the leading centralized reading center for endothelial image analysis in the United States, in part based on its experience over the past nearly 20 years with the NEI-supported Specular Microscopy Ancillary Study (SMAS) and the Cornea Preservation Time Study (CPTS), leading to numerous publications and providing key insights into the donor, recipient, operative, and postoperative factors that influence ECL following PKP (SMAS) and DSAEK (CPTS). The CIARC will perform dual grading and adjudication, when required, of each image using established methods for determination of endothelial cell density and morphometric parameters. The CIARC will perform eye bank (2) and clinical site (5) training, external calibration for specular microscopes as well as eye bank and clinical site technician certification (minimum of 2 technicians per site). The CIARC will analyze 3 eye bank screening images of the central donor endothelium and 3 images of the grafted central endothelium postoperatively at 6, 12 and 24 months for the 220 study eyes for a total of 2,640 images.

[name] is the Charles I Thomas Professor and Vice Chair for Academic Affairs in the CWRU Department of Ophthalmology and Visual Sciences and has been the Medical Director of the Cornea Image Analysis Reading Center (CIARC) since 1988. He served as Medical Director for the CIARC for the NEI-funded Specular Microscopy Ancillary Study (SMAS) and the Study Chair as well as Medical Director for the CIARC in the NEI-funded Cornea Preservation Time Study (CPTS). For the DETECT, as Medical Director of the CIARC, he will have the following responsibilities similar to his activities for the CPTS: 1) participate in the scientific plan for the DETECT; 2) oversee administrative functions outlined in the CIARC Operations Manual; 3) will interface with clinical sites and eye banks when direct physician contact is mandated; 4) review Scientific Director (CIARC) prepared reports to the Clinical Coordinating Center, Data Coordinating Center, DSMC, and the NEI; 5) meet on a weekly basis with the Scientific Director (CIARC) to review conduct of the study; 6) participate on regular Steering Committee calls of the DETECT administrative team; and 7) participate in data analysis, manuscript preparation, and presentations in conjunction with the to the Clinical Coordinating Center, Data Coordinating Center, DSMC, and the NEI.

10.1.6 SAFETY OVERSIGHT

A Data and Safety Monitoring Committee (DSMC) has been empaneled by the NEI. This committee consists of 5 individuals, and includes (a) cornea specialists, (b) an independent biostatistician, (c) a bioethicist, and (d) representation from all participating sites. The committee will meet in person at least once per year, and will convene biannual teleconferences for progress reports. *Ad hoc* meetings as needed may also be convened. All study protocols will be subject to review and approval by WCG IRB as the single IRB of record. Please see **Section 9.4.6** of this protocol for a detailed description of our planned interim analysis.

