160 participants with moderate to severe Fuchs (DETECT I) and 60 participants with mild Fuchs (DETECT II) will be enrolled at Oregon Health & Science University, Stanford University, University of Pennsylvania, University of California Davis, and at Dartmouth-Hitchcock Medical Center. We anticipate participants from each enrollment site will match the demographic makeup of the city the site is located in. Therefore, our study population will be mostly White (non-Hispanic), Hispanic, African-American, and Asian based on the most recent census data for each enrollment area. There is evidence that endothelial dystrophy is more common in women, and the previous DETECT-Therapeutic Exploratory Study (TES) enrolled 58% women. We anticipate a similar gender makeup in this study. In the DETECT-TES the median age of study participants was 67, with an interquartile range of 64 to 71; we expect a similar age range in this study.

Phase:

N/A

Description of Sites/Facilities Enrolling Participants:

Participants will be enrolled at five sites in the United States: Oregon Health & Science University (Portland, OR), Stanford University (Palo Alto, CA), University of Pennsylvania (Philadelphia, PA), University of California Davis (Davis, CA), and Dartmouth-Hitchcock Medical Center (Lebanon, NH). Patients will be enrolled at the Cornea Clinic in each hospital.

DETECT

Version 5.0
21 March 2023**Description of Study
Intervention:****DETECT I**

Study participants will all undergo endothelial keratoplasty followed by an adjuvant topical medication post-operatively. Participants will be randomized to one of four treatment groups in this 2x2 factorial design study:

		Endothelial Keratoplasty	
		UT-DSAEK	DMEK
Adjuvant Topical Medication	Ripasudil 0.4%	UT-DSAEK + 0.4% ripasudil	DMEK + 0.4% ripasudil
	Placebo	UT-DSAEK + placebo	DMEK + placebo

All patients will be randomized to undergo one of two types of endothelial keratoplasty. All patients will be randomized to receive either topical ripasudil 0.4% or topical placebo. Patients will begin topical medicines post-op day 1. They will take their assigned study medication 4x/day for 3 months.

DETECT II

[figure not shown]
[figure not shown]
[figure not shown]
[figure not shown]
[figure not shown]
[figure not shown]

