9.4.6 PLANNED INTERIM ANALYSES

A Data and Safety Monitoring Committee (DSMC) has been empaneled by the NEI. This committee consists of 5 individuals, and includes (a) cornea specialists, (b) an independent biostatistician, and (c) a bioethicist. The committee will meet in person at least once per year and will convene biannual teleconferences for progress reports. *Ad hoc*

DETECT

Version 5.0
21 March 2023

meetings as needed may also be convened. All study protocols will be subject to review and approval by Institutional Review Boards.

The Data and Safety Monitoring Committee will meet to review the interim efficacy data for each trial when primary outcome data is available on one third of the study subjects. The DSMC will make one of the following recommendations:

- Continue the trial without modifications
- Continue the trial with study modifications
- Terminate enrollment or treatment in the trial because of safety concerns
- Terminate enrollment or treatment in the trial because of efficacy
- Terminate enrollment or treatment in the trial because of futility

Interim reports for the DSMC will be prepared by the Data Coordinating Center. These reports will include (a) recruitment overall, and by study site, (b) compliance, and (c) retention. The reports will also list study outcomes, and all adverse outcomes, including medication side effects, primary graft failure, graft rejection, and mortality. The DSMC will determine the database closure dates for each report in advance; archival copies of the (a) main database, and (b) study analysis files as they exist at the time of each report will be maintained. All reports will be sent using secure email to the members of the DSMC two weeks prior to each meeting.

The DSMC will make decisions with the benefit of pre-specified decision guidelines. These guidelines will be agreed upon at the initial meeting, and are expected to include (a) safety, (b) efficacy, (c) clinical importance, (d) effect of baseline covariates, or (e) validity.

We propose the same interim analysis approach for both DETECT I and DETECT II trials.

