Benefits. An unmasked interim analysis will be conducted to determine whether or not sufficient evidence has accumulated to justify stopping one or both factorial treatments. The guidelines for efficacy will use group sequential boundaries for judging the statistical significance of the primary outcome measure. The trial will use the Lan and DeMets flexible alpha spending approach with a power function, with $\alpha^*(t^*) = \alpha (t^*)^\theta$, where $\alpha = 3.561$ (chosen so that the two-sided P -value to stop the trial for efficacy is 0.001).⁵⁴ We propose a single interim analysis at the midpoint of the trial, i.e. when full outcome data are available for one half of the subjects. If one surgery method is clearly superior with respect to BSCVA, with no evidence for interaction with the ripasudil, then future patients will receive the better surgery method and still be randomized to ripasudil vs placebo. If ripasudil is clearly superior to placebo with respect to ECD, with no evidence for interaction by type of surgery, then future patients will receive ripasudil and would still be randomized to surgery type. At the interim analysis, tests for interaction will have very low power and so any decision to stop a single treatment early for benefit would be done in consultation with the DSMC.

Harm. Stopping one or both treatments for harm will be done at the judgment of the DSMC. Several endpoints will be examined, including (a) the best spectacle-corrected visual acuity at 12 months (b) adverse events, and especially (c) serious adverse events, including primary graft failure or mortality. While the analysis would consider maldistribution of predictive factors such as (a) age (b) visual acuity at presentation, and (c) diagnosis of PACE, it is recognized that ethical considerations require careful considerations of statistical tests as well as qualitative judgments in the light of experience.

Futility. Early discontinuation due to the unlikelihood of significant findings for both primary analyses conditional on interim results may be considered pending discussion with the DSMC.

DETECT

Version 5.0
21 March 2023

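### Sections 9.4.6 and 10.1.6 give different memberships for the same five-person DSMC, and the site representation added in 10.1.6 would compromise the independence of a committee that reviews comparative interim data

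*Protocol*

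**What the plan says.** Section 9.4.6 (Planned Interim Analyses) describes the committee as follows: "This committee consists of 5 individuals, and includes (a) cornea specialists, (b) an independent biostatistician, and (c) a bioethicist". Section 10.1.6 (Safety Oversight) describes a committee with the same convening body, size and meeting schedule, repeats the three categories and adds a fourth, "d) representation from all participating sites". It then sends the reader to Section 9.4.6 for the interim analysis, so one committee is meant. The synopsis gives the number of sites: "Participants will be enrolled at five sites in the United States".

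On the committee's work, Section 9.4.6 says "The Data and Safety Monitoring Committee will meet to review the interim efficacy data for each trial" and, under Benefits, "An unmasked interim analysis will be conducted to determine whether or not sufficient evidence has accumulated". The possible recommendations include termination for safety, efficacy or futility. Section 9.4.4 has adverse events go to the committee broken down by treatment allocation.

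On masking, Sections 4.1 and 6.3 keep the surgeon and the imaging technician at the site masked to study drug, though not to type of surgery. Sections 6.1.2, 6.5 and 6.5.1 leave the masked treating physician free to change therapy.

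**The concern.** A monitoring committee can see comparative data during a trial because its members have no part in running it. Item (d) in 10.1.6, followed as written, seats people tied to the enrolling sites on the body that reviews those data. They would be colleagues of the staff who recruit, treat, re-operate and follow up, and who are meant not to know drug allocation. A person who has seen that one arm is ahead can affect who is approached for enrolment, how readily a re-intervention is done and how hard a patient is pursued for a visit, without intending to. Early stopping on the advice of a committee with site members would also be easier to challenge.

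The two sections also cannot both serve as the membership rule. Anyone appointing, replacing or auditing a member would get a different answer from each.

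**Working it through.** The protocol states no figure to reproduce here. The check is a comparison of the two lists, a headcount, and a rough timing of what would remain to be collected.

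**Lists side by side**

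| | Section 9.4.6 | Section 10.1.6 |
|---|---|---|
| Size | 5 | 5 |
| Cornea specialists | yes | yes |
| Independent biostatistician | yes | yes |
| Bioethicist | yes | yes |
| All participating sites represented | not listed | listed |

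**Headcount.** Inputs: 5 seats (both sections) and 5 sites (synopsis).
- One member per site: 5 × 1 = 5 seats, which is the whole committee.
- Adding an independent biostatistician: 5 + 1 = 6.
- Adding a bioethicist from outside the sites: 6 + 1 = 7.
- Conversely, with the biostatistician and bioethicist both from outside, 5 − 2 = 3 seats remain for 5 sites.

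The 10.1.6 list fits five seats only if someone represents more than one site, if a member listed as independent comes from a site, or if representation means something other than membership.

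**What the committee sees.** Section 9.4.6 combines an unmasked interim analysis, committee review of efficacy data, and a judgment on whether one surgery or the drug is clearly superior. That judgment needs results by arm. Section 9.4.4 provides safety data by arm as well, on a schedule that the committee sets, so exposure need not be confined to the one interim look.

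**What would still be outstanding.** The protocol gives two interim timings: one half of primary outcome data (Section 4.1, and Benefits in 9.4.6) and one third (earlier in 9.4.6). Both are taken.

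- 12-month outcomes outstanding, by definition: 1 − 1/2 = 1/2, which is 80 of 160 in DETECT I and 30 of 60 in DETECT II; or 1 − 1/3 = 2/3, about 107 of 160 and 40 of 60.
- 24-month outcomes. Assumption: even accrual over the 24-month enrolment period, counted from surgery. With the 12-month visit at month 12, the half-way interim falls at calendar month 12 + 12 = 24. The 24-month window opens at month 20 (Section 5.5), so only patients from the first 24 − 20 = 4 months could have had that visit: 4/24 = 1/6, leaving 5/6.
- Range over the 12-month visit window (10 to 14 months): the interim falls at calendar month 22 to 26, so 2/24 to 6/24 could have had the 24-month visit, leaving 92% down to 75%.
- At one third: the interim falls at 8 + 12 = 20 (range 18 to 22), so 0 to 2/24 could have had it, leaving 100% down to 92%.

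**The case against.** The strongest case on the other side is that this is loose wording. Both lists are introduced as what the committee includes, so the shorter one need not be exhaustive. The convening body is the funder, the biostatistician is called independent in both places, and Section 10.1.12 commits to disclosing and managing conflicts of interest for everyone with a role in the trial. Representation could mean non-voting attendance. A charter may deal with access, and Section 10.1.5 on key roles and governance was not all available, so the absence of a roster or a closed-session rule cannot be asserted.

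Much of this stands, and it limits what may be concluded. Several stronger readings are tempting and should not be adopted:
- A reader might infer that the committee has lost its independence altogether. Section 10.1.6 itself keeps an independent biostatistician.
- A reader might infer that site staff fill all five seats. The same sentence rules that out by requiring that biostatistician.
- A reader might infer that the committee decides on stopping. Mostly it recommends or is consulted; only stopping for harm is left to its judgment.
- A reader might infer that every 24-month outcome follows the interim. With a half-way look, the earliest patients could already have had that visit.
- A reader might infer that individual drug assignments would reach the sites. The text supports only access to results by arm, and surgery type is already known to the surgeon.

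What does not stand is that the matter is therefore settled. A general conflict policy or a charter does not tell the reader which list is right. Section 10.1.6 names site representation as part of the committee's composition, with no limit on vote or access in that section.

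**Conclusion.** The point holds in a limited form. Two sections of the current protocol give different memberships for one five-person committee. The longer list does not fit five seats if each site has its own member alongside an independent biostatistician and a bioethicist. If people affiliated with the sites do sit on the committee, its independence is compromised and arm-level results could reach the sites while half to two thirds of the 12-month outcomes are still to come. On even accrual, about 75% to 92% of the 24-month outcomes would also be outstanding with a half-way interim, and 92% to 100% with a one-third interim.

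This rests on three assumptions: that representation means membership with the ordinary access of a member, that the committee sees results by arm (which its task implies), and, for the 24-month shares, even accrual. The effect on enrolment, re-intervention or retention is a risk and cannot be sized from the protocol. Nothing here shows who actually serves. The point is worth correcting because the risk is avoidable and the correction is cheap.

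**What to change.** Delete item (d) from Section 10.1.6 so that it agrees with Section 9.4.6. Add one sentence to both sections: DSMC members with access to comparative data are not affiliated with an enrolling site. If site input is wanted, provide for it as non-voting attendance at open sessions where only pooled, masked data are shown.

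Then check the current roster against the revised wording. If no member comes from a site, the cost is an editorial amendment. If one does, that member has to be replaced or limited to open sessions. As the National Eye Institute convened the committee, a replacement would need its agreement, so this check should be made before the interim data are reviewed.
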